### 3. Objectives & Specific Aims

**Objective:** This is a formative study to lay the groundwork for establishing a large cohort of incident colon cancer to examine the microbiome-immune relationship in colon cancer outcome. Our hypothesis is that colon cancer treatment, recurrence and survival are compromised by treatment-induced dysbiosis and dependent upon pre-treatment microbial structure. We plan to address this hypothesis with the following aims:

**Aim 1: Determine if the gut microbiome and microbial metabolites are altered in response to cancer treatment and correlate with CID incidence and severity in stage II/III colon cancer**

Sub-Aim1a: Quantify the gut microbiota prior to surgery and treatment, and at 3 time points during FOLFOX, and correlate with CID incidence and severity

Sub-Aim1b: Quantify microbial pathway abundance and fecal metabolite levels prior to, and during treatment, and determine their associations with incidence and severity of CID

Sub-Aim1c: Quantify circulating and tumor tissue cytokine levels prior to, and during treatment, and determine their associations with the gut microbiota, and incidence and severity of CID

**Aim 2: Determine if the dietary history or dietar intake during treatment is associated with CID incidence and severity in stage II/III colon cancer**

Primary outcomes: CID incidence and severity and gut microbiome and metabolome changes. The patients with colon cancer, serving as their own controls, will provide stool samples that enable clinicians to predict toxicity of anti-cancer therapy in stage II/III colon cancer patients.

Secondary outcomes: Circulating cytokines, dietary history and changes during treatment, stool index changes

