#### **4.4 Data Analysis.**

Classification of taxa associated with side effects or severity: Recently, in an animal model of colon tumorigenesis (AOM/DSS), investigators used the initial microbial community structure (16s rRNA sequencing) to predict tumor burden after exposure to various antibiotics during colon carcinogenesis. In order to conduct a similar analysis and reduce data dimensionality, we will first perform cluster modeling using Dirichlet multinomial mixtures (Holmes et al. 2012) to identify microbial clusters (community state types). To determine which taxa or taxonomic cluster are the best predictors of treatment side effects (CID, mucositis) and severity (stage 3-4), we will conduct 10-fold cross-validation using the RandomForest package (Version 3.6.4) in R (R-studio, Version 0.98.1091; Boston, MA). Specifically, 5,000 trees will be used and the parameter mtry will be set at 100. The taxa with the highest importance scores will be used for further analysis. This procedure will be tested by splitting the data into test and training sets, then running Random Forest using the same procedure described above on the training dataset and comparing the predictive accuracy of the top taxa (based on importance scores) in the test set. Based on this 10-fold cross-validation, we will be able to calculate sensitivity and specificity. These top taxa will then be used to generate receiver operator curves (ROC) and calculate area under the curve (AUC). Each microbial cluster or taxa will undergo independent logistic regression testing to calculate area under the ROC curve using Stata (v13). The command roccomp will be used to compare statistical difference between AUCs and determine the best combination of taxa for classification of CID or mucositis and for severity.

Microbiome-Diet Analysis: To evaluate the impact of diet on the stool and tissue microbiome, we will use the dietary analysis generated from the ASA24 and DHQIII, which includes the Healthy Eating Index (HEI). Prior to analysis, we will conduct normality testing for each variable using Shapiro-Wilk test. For any variables that do not pass, a logarithm transformation will be performed. In order to identify any potentially important diet or nutrient-microbiome associations, we will conduct correlation analysis between dietary macronutrients (carbohydrates, fats, proteins) or micronutrients (vitamins and minerals)

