**Community state type modeling of treatment effect:** As described earlier, in order to reduce data dimensionality and improve power (due to small sample size), we will perform cluster modeling using Dirichlet multinomial mixtures, as well as, use the partitioning around the medoid (pam in R) algorithm. To calculate the dissimilarity matrix for this analysis, we will first calculate weighted UniFrac distance, then this matrix will be dimensionally reduced by choosing the most significant eigenvectors from PCoA analysis. Community state types (CST), which are defined as 'clusters of community samples with similar compositions of microbial taxa', will be obtained from this analysis. Statistical difference in CST abundance between treatment and baseline will be conducted using median values. Plots of CSTs for each subject over time will be used to identify associations between CSTs and incidence of CID, mucositis and severity of side effects. In order to model the dynamics of the CST transitions, we will use Markov chain to estimate the transition probabilities, as demonstrated for vaginal CST associated with pre-term birth. Transition rates between CSTs for each set of paired samples will be calculated using maximum-likelihood estimates. Additionally, differential relative abundance analysis of CSTs between baseline (pre-surgery and pre-treatment) and treatment time points will be conducted using linear mixed models to account for the repeated measurements at the 4 time points and missing observations. To evaluate differences in beta diversity between treatment and baseline the PERMANOVA test will be used. The inferred function of the microbiota will be obtained using the bioinformatics tool PICRUSt, which uses 16S rRNA marker genes to predict presence of gene families and construct a composite metagenome. This method has been used successfully in several similar studies to predict key metabolic functions associated with taxa important in distinguishing disease from healthy controls.

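### The on-treatment course of community state types is linked to chemotherapy-induced diarrhea only by looking at per-patient plots, so that one link has no estimate, interval or error control

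*Protocol*

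**What the plan says.** Section 3 sets Aim 1 as whether the gut microbiome and metabolites are "altered in response to cancer treatment and correlate with CID incidence and severity". Sub-Aim 1a is to "Quantify the gut microbiota prior to surgery and treatment, and at 3 time points during FOLFOX, and correlate with CID incidence and severity". The hypothesis in the same section is that colon cancer treatment, recurrence and survival are "compromised by treatment-induced dysbiosis and dependent upon pre-treatment microbial structure". CID incidence and severity are primary in section 3 and again among the endpoints in section 4.3.

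In section 4.4, the paragraph on community state type modeling of treatment effect states how the CST course is to be related to side effects: "Plots of CSTs for each subject over time will be used to identify associations between CSTs and incidence of CID", with mucositis and severity added in the same sentence. It then describes the course itself: "In order to model the dynamics of the CST transitions, we will use Markov chain to estimate the transition probabilities". Finally, the comparison of CSTs between baseline and "treatment time points will be conducted using linear mixed models to account for the repeated measurements at the 4 time points and missing observations". Neither the Markov chain nor the mixed model is said to include CID.

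Elsewhere in section 4.4, the paragraph on classification of taxa says: "Each microbial cluster or taxa will undergo independent logistic regression testing", to obtain areas under the ROC curve for CID, mucositis and severity. The sample time point is not given. The Metabolite-CID paragraph plans logistic regression of CID on metabolites at baseline and at each time point, with FDR below 0.05.

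**The concern.** The plan gives the plots an inferential task, finding associations with a primary outcome, and names no model, test or interval for it. A pattern judged by eye across as many as 112 patients, several CSTs, repeated visits and three side-effect outcomes has no effect size. Nor is there any stated chance of being wrong. Equally, a true difference in on-treatment CST change between patients with and without CID could be present in the data and never be tested.

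This matters because repeated stool collection during FOLFOX is a main burden on patients and is what allows change to be studied at all. The plan applies FDR control to its time contrasts, its diet analyses and its metabolite-CID models. Leaving this link to inspection falls below the standard it sets for itself.

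**Working it through.** The plan gives no figure for this point, so the check is an inventory of section 4.4. For each analysis, does it use change or course over time, does it contain CID, and does it give an estimate or error control?

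| Paragraph of section 4.4 | Analysis | Uses change or course | Contains CID | Estimate or error control |
|---|---|---|---|---|
| Classification of taxa | Random forest; logistic regression and AUC per taxon or cluster | No; time point not stated | Yes | AUC, sensitivity, specificity; 10-fold cross-validation |
| Microbiome-Diet | Log2 fold change of clusters from baseline, by dichotomised macronutrients | Yes | No | FDR named in the paragraph |
| Microbiome-treatment | DESeq2 against baseline, then adjusted regression | Yes | No; not among the listed covariates | FDR |
| CST modeling | Per-subject plots | Yes | Yes | None |
| CST modeling | Markov chain | Yes | No | Maximum-likelihood transition rates |
| CST modeling | Comparison of medians, linear mixed model, PERMANOVA | Yes | No | Model- or test-based |
| Metabolite-CID | Logistic regression at baseline and each time point | No; levels | Yes | FDR below 0.05 |
| Metabolite-CID | PCA and PLS-DA, CID versus no CID | No | Yes | Tenfold cross-validation (PLS-DA) |
| Metabolite-CID | Adjusted mixed model of metabolites that changed | Yes | Not stated | Model-based |
| Microbiome-Cytokine | Kruskal-Wallis across CSTs by time point, mixed models | Partly | No | Test- or model-based |

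Counts:
- Analyses that contain CID: 4.
- Of these, analyses that use the course over time: 1, the plots.
- Of these, analyses with an estimate or error control: 0.

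The Microbiome-Diet row shows that the plan already defines a change-from-baseline variable for clusters. It relates that variable to diet and not to CID.

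**Illustration 1, uncontrolled looks.** Assume 3 to 5 CSTs, each compared with CID at the 3 on-treatment visits, and suppose every look were independent and held to a 5% error. That is 3 × 3 = 9 to 5 × 3 = 15 looks. The chance of at least one false association is 1 − 0.95^9 = 0.37 to 1 − 0.95^15 = 0.54. The number of CSTs, the independence and the 5% level are assumptions. Reading plots has no defined error level, so this shows only why some control is needed. It does not measure the plan's actual error rate.

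**Illustration 2, what a formal comparison could see.** Inputs: 112 patients (section 4.2 material on sample size) and CID in 50%, set from the statement in section 2 that CID affects more than half of patients. This gives n = 56 per group. With p and q the shares of patients who change CST in the two groups, and p̄ their mean, power = Φ{ [ (q − p) − 1.96 √(2p̄(1 − p̄)/n) ] / √( [p(1 − p) + q(1 − q)]/n ) }. For p = 0.20 and q = 0.445, p̄ = 0.3225. The numerator is 0.245 − 1.96 × 0.0883 = 0.072 and the denominator is 0.0853. The ratio is 0.84, so power is about 80%. In the same way, 30% versus about 56% and 40% versus about 66% reach 80%. The values of p are assumed. A formal test is feasible at this size for differences of about 25 to 26 percentage points, before any multiplicity adjustment.

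**The case against.** The strongest reply has four parts.

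**Aim 1 is formally analysed elsewhere.** A reader might infer from the plots sentence that Aim 1 gets no estimate and no error control. The protocol does not support that. Clusters and taxa are related to CID, mucositis and severity by cross-validated random forest, logistic regression and comparison of AUCs. Metabolites, which belong to Aim 1, have logistic models against CID at every time point with FDR control. The Metabolite-CID paragraph also says it follows a Microbiome-CID analysis, which suggests that the cluster models may be run by time point too. This stands. It still leaves levels, not change, as the exposure.

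**The aim may not ask for change.** A reader might take Aim 1 to ask whether treatment-induced change predicts CID. Its wording asks whether the microbiome is altered and correlates with CID. The hypothesis on treatment-induced dysbiosis names treatment, recurrence and survival, not CID. This also stands, and it limits the point to the CST course, for which the protocol itself announces an association with CID.

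**This is a formative study, and a statistical analysis plan may supply the model.** Exploratory plots followed by modelling are ordinary practice, and an absent detail would be no finding. Here, however, the method is stated, and it is not suited to the use stated. The modelling that follows the plots does not bring in CID.

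**Percentages for false findings depend on arbitrary choices.** This is correct. They vary with the number of CSTs, the cutoff for a visible difference and outcome rates that the protocol does not give. They are used above only as illustration.

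**Conclusion.** The point holds for one link. In section 4.4, the course of CSTs during FOLFOX is connected to CID, mucositis and severity only by inspecting per-subject plots. None of the four analyses that contain CID both uses that course and gives an estimate. That link therefore has no effect size, interval or error control.

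It does not extend to Aim 1 as a whole, for the reasons given under the objection. The conclusion rests on the text of section 4.4 and on no assumed number. It would change only if a document not shown here put CID into the Markov or mixed models. The consequence is moderate: a relation that the protocol says it will identify, with a primary outcome, would be reported on impression although the data allow a formal analysis.

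**What to change.** Reword the plots sentence so that the per-subject CST plots are descriptive only. Then name one longitudinal analysis as the main link between CST course and CID, chosen from:

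1. **Difference in course by CID status.** Add CID and CID-by-time to the linear mixed model already planned for CSTs.
2. **CID given the preceding community.** Fit a logistic GEE or mixed model of CID at Visits 3 to 5 on the CST of the preceding stool and its change from the pre-FOLFOX stool, with visit as a term.

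These are different estimands and not interchangeable. The first describes how the microbiome moves in patients with and without CID. The second is closer to predicting CID, which section 3 gives as a purpose of the stool samples. Whichever is chosen:

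- State which stool sample goes with which CID assessment. Section 4.3 has CID asked at the visit, and stool collected both the day before the infusion and on the second day after the round ends.
- Report estimates with intervals.
- Apply the FDR control used elsewhere in section 4.4 and state its threshold, since that section uses 0.1 in one place and 0.05 in others.

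The change is to analysis wording and uses data already to be collected. The cost is a few extra model terms and probably some merging of sparse CSTs. With an assumed 5 CSTs, 112/5 gives about 22 patients per CST at a visit, and about 11 of them with CID at an assumed 50%, before missing samples. Any percentage for false associations should be left out of the plan or labelled as illustrative.

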and microbial clusters (community state types) at baseline using Kruskall-Wallis, and for individual taxa using Pairwise Spearman correlations. We will use PERMANOVA for comparing beta-diversity (weighted UniFrac distances) at baseline by levels of macro- and micronutrients. DESeq2, Kruskall-Wallis and Mann-Whitney tests will be conducted to identify significant differences in tissue and stool taxa or microbial clusters according HEI scores at baseline. The Benjamini and Hochberg false discovery rate (FDR) will be used to correct for multiple testing. Taxa or microbial clusters found to be significantly differentially abundant between treatment time points and baseline will be used to conduct 'random forest' modeling, as previously described, to identify dietary factors that best predict changes in these taxa or clusters. Additionally, we will investigate the tissue and stool microbiome-diet relationship using principal components analysis to identify significant trends among the dietary factors using coinertia analysis. To investigate the microbiome-diet relations during treatment, we will use the microbial clusters and calculate the  $\log_2$  fold change in the clusters from baseline. We will then determine how much the clusters change from baseline according to dichotomous values of macronutrients.

**Microbiome-treatment analysis:** To evaluate differential abundance comparing treatment time points to baseline (prior to surgery and post-surgery/pre-treatment), DESeq2 will be used to control operational taxonomic unit (OTU) over-dispersion between replicates; OTUs will be considered significantly differentially abundant between time points if the false discovery rate (FDR) corrected p-value is below 0.1. A change in relative abundance will be defined as a fold change between mean log relative abundance during treatment phase (week 4, 14, 24) and baseline (prior to surgery). Taxa found to be significantly differentially abundant between treatment time points and baseline (FDR corrected p-value  $<0.05$ ) will be put into an adjusted regression model to control for age, education, income level, marital status, and activity level, diet quality (HEI), tumor stage, medical history with p-values corrected for multiple hypothesis testing using FDR adjustment.

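### Three planned analyses treat community state types as a continuous abundance, but the protocol defines them as a label on each sample

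*Protocol*

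**What the plan says.** All the relevant text is in Protocol Section 4.4.

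**What a CST is.** Under the community state type heading, the definition is "clusters of community samples with similar compositions of microbial taxa". Two methods produce the clusters: "we will perform cluster modeling using Dirichlet multinomial mixtures", and the authors will also "use the partitioning around the medoid (pam in R) algorithm". The opening classification paragraph uses Dirichlet mixtures "to identify microbial clusters (community state types"), so microbial clusters and CSTs are the same object.

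**Where a CST is used as a category.** The CST paragraph plans per-subject plots of CSTs over time and a Markov chain, with transition rates between CSTs estimated by maximum likelihood from paired samples. The diet paragraph uses Kruskal-Wallis for nutrients and clusters at baseline. The cytokine paragraph compares cytokines across CSTs by Kruskal-Wallis.

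**Where a CST is used as a quantity.** There are three places:
- CST paragraph: "Statistical difference in CST abundance between treatment and baseline will be conducted using median values".
- CST paragraph: "differential relative abundance analysis of CSTs between baseline (pre-surgery and pre-treatment) and treatment time points will be conducted using linear mixed models".
- Diet paragraph: a log2 "fold change in the clusters from baseline", then examined by dichotomised macronutrient intake.

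**The concern.** The three quantitative analyses need a number for how much of a CST a sample contains. The definition supplies only which CST a sample belongs to, and the protocol nowhere says what number is meant.

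CSTs are the protocol's stated means of reducing dimension and gaining power in a small study. If the treatment-versus-baseline comparison of CSTs rests on a summary that does not fit the variable, that gain may not materialise. The problem also carries forward. The diet paragraph sends clusters found differentially abundant between treatment and baseline into random forest modelling of dietary factors, and for clusters that selection step has no well-defined test behind it.

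**Working it through.** No stated figure depends on this point, so there is none to reproduce. The check has two parts: which per-sample quantity the definition yields, and how each planned analysis behaves on it.

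**Step 1. The quantity available.** The thing clustered is the sample. PAM assigns each sample to exactly one cluster. Dirichlet mixtures also give membership probabilities, but the protocol does not name these as an outcome. For a given CST, the per-sample value that follows from the definition is therefore an indicator: 1 if the sample belongs, 0 if not.

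**Step 2. Within-patient log2 fold change.** Formula: log2(treatment value / baseline value).

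| Baseline | Treatment | log2 ratio |
|---|---|---|
| 1 | 1 | 0 |
| 0 | 1 | +infinity |
| 1 | 0 | -infinity |
| 0 | 0 | undefined |

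No pair gives a finite non-zero value. If the ratio is instead formed from a cluster's prevalence in a group of patients, it is finite. With assumed prevalences of 20% and 45%, log2(0.45/0.20) = log2(2.25) = 1.17. The protocol does not state that reading.

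**Step 3. Medians.** The median of a 0/1 variable is 1 when more than half the values are 1 and 0 when fewer than half are. I use the planned n = 112 (Protocol Section 5). The prevalences are assumptions, because the protocol gives none.

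| Baseline prevalence | Treatment prevalence | Change | Medians |
|---|---|---|---|
| 20% | 45% | +25 points | 0 and 0 |
| 10% | 40% | +30 points | 0 and 0 |
| 45% | 55% | +10 points | 0 and 1 |
| 30% | 60% | +30 points | 0 and 1 |

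The median misses shifts of 25 and 30 points that stay below one half, and flips on a shift of 10 points that crosses it.

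**Step 4. Linear mixed model.** On a 0/1 outcome this is a linear probability model. It can be fitted, and its visit coefficient is a change in proportion, for example 0.45 - 0.20 = 0.25. The fit to the data is poor, however. The variance of an indicator is p(1 - p), which here is 0.20 x 0.80 = 0.16 at baseline and 0.45 x 0.55 = 0.2475 on treatment, so constant residual variance fails whenever prevalence moves in this way. Fitted values can leave the 0 to 1 range. The indicators for the different CSTs also sum to 1 in every sample, so separate models for each CST are not independent.

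**The case against.** The strongest reply is that the protocol already contains a suitable analysis of CST change. The Markov transition model uses paired samples and discrete states, and the Kruskal-Wallis uses treat CSTs properly as groups. This stands. A reader might infer that the plan has no valid way to study CST change; the document does not support that. The transition model does describe change, although the text names estimation of transitions and no hypothesis test of treatment against baseline.

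A second reply is that the quantities are not impossible. Dirichlet mixtures give continuous membership probabilities, and a linear mixed model on membership estimates a real difference in proportions. This also stands, so it would be too strong to say that no such quantity exists. But the protocol does not name membership probability as the outcome, and PAM does not supply one.

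A third reply is that the diet paragraph does not say the fold change is formed patient by patient. That is correct. A reader might infer that every patient who switches CST is lost from that analysis; this follows only if a within-patient ratio of hard labels is assumed.

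A fourth reply is loose terminology: Section 4.4 speaks of taxonomic clusters in one place, and a group of taxa would have a summed abundance. That reading conflicts with the stated definition, "Community state types (CST), which are defined as 'clusters of community samples with similar compositions of microbial taxa', will be obtained from this analysis".

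Finally, the choice of CST measure could be left to an SAP. Silence on the measure would be acceptable in a protocol. Here, however, the protocol itself fixes methods that do not fit its own definition.

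**Conclusion.** The point holds for three analyses: the median comparison, the linear mixed model and the log2 fold change of the clusters. Each treats a CST as a continuous abundance that the protocol does not define. They differ in degree. A within-patient fold change of membership is never finite and non-zero; the median registers only whether prevalence crosses 50%; the linear mixed model is computable but ill suited.

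These conclusions rest on reading a CST as a hard label, as the definition, PAM and the Markov model all imply. The median examples also rest on assumed prevalences.

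The reach is limited. The sample size is based on two-group differences in the abundance of taxa, and the primary data endpoint in Section 4.3 is the incidence, duration and severity of chemotherapy-induced diarrhoea. Neither depends on this. Section 3 does list gut microbiome change among the primary outcomes, but the DESeq2 and PERMANOVA analyses address that without CSTs. The text should be corrected before the data are analysed.

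**What to change.** - Replace the median and linear mixed model comparisons of CSTs with a logistic or multinomial mixed model (or GEE) of CST membership, with visit as a factor and patient as the cluster. Report proportions or odds by visit.
- In the diet analysis, replace the log2 fold change in clusters with the same model plus a diet-by-visit term.
- Keep linear mixed models and fold changes for taxa or ordination axes, where a continuous value exists.
- Keep the Markov transition analysis and the use of CSTs as groups unchanged.
- If a continuous measure was intended, such as the Dirichlet membership probability or the summed abundance of a named set of taxa, define it explicitly and use a model suited to a bounded outcome.

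The cost is analysis wording only: no new data, visits or patients.
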